The payments are reasonable and commensurate with the expected contributions of the subject. Each annual study visit is 2-3 hours. Baseline and annual visits include a fasting blood draw, height, weight, blood pressure, questionnaires, performance tests, and DXA. The procedures at every 6 month study visits (in between annual visits) are only fasting labs and questionnaires for all participants. For the muscle biopsy substudy, there will be a separate 1-2 hour visit at baseline and an additional 1 hour added to the 6 month visit.

Payments are fair and appropriate and do not constitute (or appear to constitute) undue pressure or influence on, or coercion of, the prospective research subjects to volunteer for or continue participation in the research study.

Statistical considerations

Sample Size and Power

Based on prior observational findings, there was a significant difference (2.2%, p< 0.01) in the percentage change in appendicular lean mass over 3.5 years between metformin-treated and untreated men. The sample size required for 80% Power to detect this difference and reject the null with SD=4% and α =0.05 for an unpaired, 2-sided t-test is 106 study participants (53 in each group). We plan to enroll 300 participants and, of those, randomize 120 (60 in each group) to allow for potential drop outs due to noncompliance and other reasons (7.5-10%). While 8-11% of participants may

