progress to diabetes yearly,^{72, 79, 80} all efforts will be made to retain these participants in the study and to include them in intent-to-treat analyses. The Power and effect size estimates for gait speed (SD=0.19) for α =0.05 for 60 participants and 53 participants per group are illustrated in the graph (Fig. 8) and based on our preliminary data in older women. The sample size of 60 participants per group will have 73% Power to detect a 0.09 m/s difference in gait speed. Within each group, 16 participants will be randomly selected and consented to undergo muscle biopsies at baseline and 6 months for secondary analyses of muscle histologic changes with metformin vs. placebo treatment. There is an expected change in these histologic measures within 6 months given prior studies that detect changes in AMPK activation, ATP concentration and insulin sensitivity prior to 6 months with use of metformin.^{3, 4} Estimated effect sizes of the difference in histologic measures between the two groups after 6 months are shown below in Table 3. While this study is adequately powered for 3 year outcomes in muscle loss, interim analyses may be performed by a Data Monitoring Committee (managed by the VA CSRD), given blinding of the primary investigator to the intervention, and the trial may be terminated early if a significant difference in the primary outcome between metformin- and placebo-treated groups is noted before 3 years.

	SD	70%	80%	90%
Capillary Density (AU)	0.35	0.32	0.36	0.42
IMCL (AU)	0.50	0.46	0.51	0.59
SDH (AU)	0.50	0.46	0.51	0.59
% Type I Fibers	24.0	21.8	24.6	28.4

Table 3 Estimated detectable difference in muscle histology measures at 80 and 90% Power

SD derived from measures in older insulin-resistant adults³⁶

Statistical Analyses

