To assess a difference in the primary outcomes of change in muscle mass and performance between metforminand placebo-treated groups, longitudinal (mixed effects) models will be used to estimate the trajectory of change. These models will account for correlation of outcomes within subjects and allows for those with missing followup data to be included in analyses. Four measures of muscle mass and performance (baseline, year 1, 2 and 3) are the outcomes in separate models. These will be modeled as a linear change over time, and other functional changes (squared, cubic and quadratic) will be evaluated. In the best fitting model, an interaction between time and group (metformin vs. placebo) will be included in the model to determine if changes in muscle mass/performance differ between the two groups. For the secondary outcomes of muscle histology, the discrete change in measures of mitochondrial content, muscle capillary density, percentage of fiber types and intramyocellular lipid content over 6 months will be calculated. The absolute and percentage changes in these measures will serve as the outcome in linear regression models with treatment group as the dichotomous exposure. Nonlinear associations between the exposure and outcomes will be evaluated with higher order terms. For the analyses of primary and secondary outcomes, potential confounders including demographic information, physical activity, diet, lifestyle factors, medical history and medication use are expected to be evenly distributed between the groups in a random fashion; nevertheless, we will evaluate for potential confounding by these factors and include them in multivariable models if they are significantly associated with our exposure and outcome and modify the effect size by >10%. There is no anticipated gender difference in the study outcomes, so the study has not been powered to detect a significant interaction by gender. However, the primary and secondary outcomes will also be stratified by gender to explore if there is a gender-specific muscle response to metformin. To account for missing data, multiple imputation modeling will constructed from participants with complete data. Participants with missing data will have those values imputed at each time point multiple imputation.⁸² Results will be reported with and without imputed values.

Data Integrity

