Potential benefits to participants include the detection and potentially earlier treatment of diabetes mellitus. Participants in both metformin and placebo groups will benefit from routine lifestyle modification counseling at yearly visits for prevention of diabetes.

Others may benefit from a greater understanding of the effect of metformin on muscle mass and function in insulin-resistant older adults.

VA Data Monitoring Committee (DMC)

A data monitoring committee will be provided by VA CSR&D. With DMC's experience in the conduct and monitoring of clinical trials, it will assist with ensuring the overall safety of study participants, assessing safety and efficacy of the study intervention, monitoring the overall conduct of the clinical trial including recommendations on recruitment and retention of participants and improvement of study drug adherence, and providing recommendations on stopping or continuation of the trial. SAEs and UPRs will be reported to the DMC. For further details, see the "Instructions for the Review of New (uninitiated) Protocols by DMC Members."

Inclusion of Women and Children

Because sarcopenia is a condition of older age, children will not be enrolled in this study. Women will be included in a proportion reflective of their gender distribution at the VAPORHCS.

Criteria for Discontinuation

Subjects will be withdrawn from further study drug administration in the event of any of the following:

• Diagnosis of diabetes

- If hospitalized for any reason and after 48 hours of discharge, there is evidence of renal dysfunction
- If they require contrast medium and after 48 hours of procedure, there is evidence of renal dysfunction
- Developed lactic acidosis
- Developed renal insufficiency at the level indicated by the FDA ($eGFR < 45 \text{ mL/min}/1.73 \text{ m}^2$).
- Development of B12 deficiency
- Excessive alcohol intake
- Subject withdraws consent
- Significant deviation from the protocol or eligibility criteria in the opinion of the investigator
- Any other reason that in the opinion of the investigator, would justify removing the subject from the study

There are no pre-defined stopping rules for termination of the study.

VA Research:

The following are the components of the study which will be conducted at the VAPORHCS:

- Advertising
- Recruitment
- Study visit activities at Screening, Baseline, half-yearly visits, and annual visits
 - Consent
 - Height, weight
 - o Blood pressure
 - Demographics
 - Medical history

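### The plan explores a gender-specific response by stratifying on gender and has no treatment-by-gender term, so the difference between the effects in men and women is never estimated

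*Combined protocol and SAP*

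**What the plan says.** The Statistical Analyses section expects no gender difference in the outcomes and states that the study was not powered for an interaction by gender. It then adds that "the primary and secondary outcomes will also be stratified by gender to explore if there is a gender-specific muscle response to metformin". The only interaction it specifies is between time and treatment group. No treatment-by-gender term (with or without time), no estimate of the gender difference and no rule for reading the two strata appears anywhere in the document.

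The number of women is not fixed. Under Inclusion of Women and Children, "Women will be included in a proportion reflective of their gender distribution at the VAPORHCS", with no figure and no minimum. The Study Drug section describes covariate-adaptive randomization that includes gender. That balances women between the arms but does not add to their number.

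The planning figures are in Sample Size and Power. For lean mass, "there was a significant difference (2.2%, p< 0.01) in the percentage change in appendicular lean mass over 3.5 years"; with SD 4% and two-sided α = 0.05 the plan arrives at 106 participants (53 per group) for 80% power and randomizes 120. For gait speed (SD 0.19), "The sample size of 60 participants per group will have 73% Power to detect a 0.09 m/s difference in gait speed".

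**The concern.** Two separate analyses answer two separate questions: is there an effect in men, and is there an effect in women? Neither answers whether the effects differ. When one stratum is much smaller, its power is much lower, so the same true effect will often reach significance in the large stratum and miss it in the small one. Anyone looking for a gender-specific response in those two results could then report that metformin works in men but not in women when the data contain no such evidence. The stratification covers all primary and secondary outcomes, so the opportunity for that misreading recurs many times. What is at stake is the reading of an exploratory subgroup result. The primary comparison and the sample size are not affected.

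**Working it through.** **Inputs from Sample Size and Power.** Lean mass: difference 2.2 points, SD 4%. Gait speed: difference 0.09 m/s, SD 0.19. Two-sided unpaired t-test at 0.05; 120 randomized 1:1; 106 required.

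**Assumptions.** The share of women is not in the documents; I take 4 to 12 of the number analysed, with 24 and 60 of 120 for contrast. Each gender is split equally between arms, and effect and SD are the same in both sexes.

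**Reproducing the plan's figures.** With the noncentral t distribution, 53 per group gives 80.1% power for lean mass (stated: 80%), and 60 per group gives 73.0% for gait speed (stated: 73%). Both reproduce.

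**Power by stratum.** With n per arm in a stratum, the noncentrality is δ / (SD × √(2/n)) on 2n − 2 degrees of freedom. For 12 women of 120, lean mass:
- Men, n = 54: 2.2 / (4 × √(2/54)) = 2.86, power 80.8%.
- Women, n = 6: 2.2 / (4 × √(2/6)) = 0.95, power 13.9%.

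The strata are independent, so P(significant in men, not in women) = power in men × (1 − power in women) = 0.808 × 0.861 = 0.70.

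| Lean mass, 120 analysed | Power, men | Power, women | Men significant, women not |
|---|---|---|---|
| 4 women | 84% | 6% | 78% |
| 12 women | 81% | 14% | 70% |
| 24 women | 76% | 25% | 57% |
| 60 women | 55% | 55% | 25% |

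**Sensitivity of the last column, 4 to 12 women.**
- Lean mass, 106 analysed: 73% to 65%.
- Gait speed, 120 analysed: 67% to 61% (51% with 24 women).
- Gait speed, 106 analysed: 62% to 55%.
- True lean-mass effect 1.65 points: 56% to 51% with 120 analysed, 51% to 46% with 106.
- True lean-mass effect 1.1 points: about 24% to 29% across both sample sizes. Significance in neither gender is then the usual result (about 65% with 120 analysed).

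**Precision of the proposed estimate.** The SE of the gender difference in effect is SD × √(2/n_men + 2/n_women), with n per arm:
- 4 women of 120: 4 × √(2/58 + 2/2) = 4.07 points; detectable at 80% power: (1.96 + 0.84) × 4.07 = 11.4 points.
- 12 women of 120: 4 × √(2/54 + 2/6) = 2.43 points; detectable: 2.80 × 2.43 = 6.8 points.

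When the effects are identical, a 5%-level interaction test signals a difference in 5% of trials.

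**Biopsy substudy (16 per arm).** With k women among 60 per arm and simple random selection of 16, the chance that an arm has none is C(60−k, 16) / C(60, 16). For k = 2 this is (44 × 43) / (60 × 59) = 0.534, so at least one arm has none with probability 1 − (1 − 0.534)² = 78%. For k = 6 the corresponding figure is 26%. A stratified histology regression could not then estimate a treatment effect in women.

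**The case against.** Four objections deserve an answer.

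*No decision rule is stated.* A reader might infer that the plan will call a response gender-specific when men reach significance and women do not. The text does not say so; it says only that the strata will be explored. This objection stands: the percentages above describe a misreading that the plan leaves open, not a procedure it prescribes. The missing estimate of the gender difference remains a gap however the strata are read.

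*The limitation is disclosed.* The plan labels the analysis exploratory and says it lacks power for a gender interaction. That is fair, and it keeps the point away from the primary analysis. But lack of power to test a difference is no reason to leave it unestimated.

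*The women's stratum may not be small.* A reader might take it as given that few women will be enrolled. The documents give no share, so this is an assumption. At equal numbers the pattern falls to 25%. It exceeds half of trials up to 25% women for lean mass and 20% for gait speed with 120 analysed, if the planned effects are true.

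*The interaction solves little.* With 4 to 12 women, power to detect a complete absence of effect in women is only about 8–15%. A poor estimate in women, including one with the wrong sign, is sampling error that no model term removes. This also stands. The gain is an interval that shows openly how little the data can say, which two separate p-values do not show.

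**Conclusion.** The point holds as a shortcoming in an exploratory analysis: the stated question concerns a difference between effects, and no planned analysis estimates it. If 4 to 12 of the participants analysed are women, the planned lean-mass effect is true and equal in both sexes, and the strata are read by significance, a spurious men-only pattern would be the usual result (65–78%, depending on whether 106 or 120 are analysed). At a true effect of 1.65 points it is close to an even chance, and at 1.1 points it is no longer the usual result. The calculations use the plan's own t-test on change. The mixed model may shift power in both strata, but the imbalance between them remains. The documents do not support reading this as a flaw in the primary comparison or the sample size.

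**What to change.** In the whole-sample mixed model, add gender with its lower-order terms (gender by time, gender by group) and group by time by gender. Report the gender difference in the year-3 treatment effect with its 95% CI as the exploratory result. If a curved time trend is chosen, define this as a contrast at year 3, since it will combine several coefficients. In the histology regressions, add treatment by gender, or describe the women's data only if an arm has too few women.

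Within-gender estimates with CIs may still be shown. State that no conclusion about a gender-specific response will be drawn from within-gender p-values, and that a null interaction is not evidence of no gender difference.

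The cost is SAP wording and several additional model terms. No new data are needed, because gender is recorded at Screening. The downside is imprecision: with 4 to 12 women of 120, the detectable gender difference is about 11.4 to 6.8 points against a planned main effect of 2.2.

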At 3 and 9 month time points between annual visits, telephone surveying of medication compliance will be obtained. Any adverse events (AE) will be reviewed. A 24-hour phone number will be provided to participants to call in the event of any adverse outcome between these contact points. Additional phone calls may be made if subjects are found to be non-compliant.

All study participants will receive a telephone call to remind them to fast for 12 hours prior to their study visit.

Participants enrolled in the muscle biopsy substudy will receive a telephone call within 3 days prior to their biopsy visits to remind them to fast for 12 hours prior to the visit, to remind them to abstain from vigorous physical activity, and to ensure they are not on anticoagulant or antiplatelet medications within 7 days from the biopsy visit.

Half-Yearly Visits (6 months; Year 1 +6 months; Year 2 +6 months)

Half-yearly visits will occur at 6 Months, Year 1 + 6 Months, and Year 2 + 6 Months. All subjects will go to VAPORHCS for these visits. For those in the substudy, only for the 6 Month visit, they will also go to OHSU after labwork is drawn at VAPORHCS.

This visit could take up to 2 hours for participants (3 hours for participants in the muscle biopsy substudy at the 6 Month visit). At each half-yearly visit, all participants will have fasting labwork drawn, and have questionnaires reviewed and completed. Subjects >80 years old will get labs checked for creatinine and eGFR. Participants in the muscle biopsy substudy will undergo muscle biopsy if their morning STAT labs demonstrate platelet, INR, and aPTT levels in the normal range. Participants will be given breakfast after fasting lab work/muscle biopsy has been obtained.

Annual Visits (Years 1, 2, and 3)

These annual visits could take up to 3 hours. The participants will first get a fasting blood draw. They will then be given breakfast before proceeding with the following study measures: review and completion of questionnaires, medication inventory, physical performance tests, and whole body DXA.

Study Drug

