We have chosen to study metformin in this clinical trial due to the observation that metformin use was associated with an attenuated loss of muscle mass and function in our preliminary studies. While both metformin and thiazolidinediones can upregulate AMPK and PGC1a in muscle to increase muscle fatty acid oxidation, angiogenesis, mitochondrial biogenesis and oxidative muscle fibers for healthier-appearing muscle,^{32, 34, 68} metformin has additional benefits on mortality, microvascular and macrovascular outcomes in patients with type 2 diabetes;⁶⁹ whereas, thiazolidinediones have associated risks of adverse cardiovascular outcomes.^{70, 71}

The VA Research Pharmacy will be used to randomize, dispense, and track blinded placebo and metformin tablets in 3-month supplies. A covariate-adaptive randomization scheme will be used to ensure equal age, gender and race distributions. The investigators and study participants will be blinded to the randomization of the study drug assignments. A 90-day supply of study drug will be mailed every 3 months to participants with a pre-paid envelope for returning unused study drugs for pill counts. An additional 4-day buffer may be included to avoid lapses in study drug administration due to unforeseen complications in medication delivery and/or receipt. To minimize self-limiting gastrointestinal side effects, participants randomized to metformin will begin with an oral dose of 850 mg tablets once daily (taken with meals) for 1 month with titration up to 850 mg twice daily for the remainder of the study. We anticipate an effect on muscle using this dosage, since a significant reduction in peripheral insulin resistance occurs even with a metformin daily dosage of 750 mg.⁶¹ Furthermore, this dose was safe and effective in lowering the risk of diabetes for subjects with prediabetes in the Diabetes Prevention Program.⁷⁵ Plans for monitoring and preventing risks associated with metformin are further discussed under Human Subjects.

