^cAt 3 and 9 month time points between annual visits, telephone surveying will occur.

^dHalf-yearly visits and annual visits will occur with \pm 7 day visit window.

^eeGFR is calculated from the creatinine.

^fEvery 6 months, creatinine and eGFR will be obtained for subjects over 80 years old.

^gAt 6 months, STAT platelets, INR, and aPTT will be obtained for subjects in the substudy before the biopsy. ^hMuscle biopsy samples are for this study and for biorepository.

Adverse events

Adverse events (AEs) will be evaluated at each visit. Principal Investigator or MD Co-Investigator will determine the relation of the side effect to treatment as: 1) related, 2) possibly related, or 3) not related.

A serious adverse event (SAE) is defined as an AE that results in death, a life-threatening experience, inpatient hospitalization or prolongation of hospitalization (for a patient already hospitalized); persistent or significant disability or incapacity; congenital anomaly and/or birth defects; an event that jeopardizes the subject and may require medical or surgical treatment to prevent one of the preceding outcomes; or death.

"Unanticipated" means an event that is new or greater than previously known in terms of nature, severity, or frequency, given the procedures described in protocol-related documents and the characteristics of the study population. Unanticipated problems involving risk (UPRs) are physical, psychological, social, or economic risks to subjects or others, including device and drug effects, and anything reportable to the FDA.

All unanticipated SAEs and UPRs must be reported to the joint IRB within 5 business days of awareness, via OHSU eIRB UP form. SAEs and UPRs will also be reported to the VA Data Monitoring Committee. Copies of the report documents will be kept in the study regulatory binder.

Compensation

Subject compensation will be offered at the end of each study visit, as follows:

- \$50 at Baseline, Year 1, Year 2, and Year 3/End of Study visits
- \$50 at Baseline Muscle Biopsy visit and at 6 month visit (if in substudy)
- \$5 at 6 month; \$5 at Year 1 +6 month; and \$5 at Year 2 +6 month visits

[figure not shown]
If subject does not complete study, payment will be prorated.

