By enrolling participants without liver or kidney dysfunction or congestive heart failure, the risk of lactic acidosis or hepatitis on metformin will be decreased. Furthermore, we intend to prevent such risks by screening liver and kidney function every year in all participants and quarterly in adults aged 80 or greater and stopping metformin in participants who develop evidence of liver/kidney dysfunction for their safety. Per 2016 FDA guidelines, metformin use will be discontinued if the eGFR drops below 45 mL/min/1.73 m2. For those who are hospitalized or receive contrast medium, the drug will be held and efforts will be made to recheck kidney function within 48 hours after discharge/procedure. The study drug will be restarted only if there is no evidence of renal dysfunction. For tests or procedures that require fasting, study drug will be stopped 24 hours prior to test or procedure, and study drug can be resumed after the participant is allowed to eat again. Participants with B12 deficiency will not be enrolled in the study, and B12 levels will be monitored throughout the study. If B12 deficiency is found, the participant will discontinue study drug. Initial weight loss due to gastrointestinal symptoms is usually self-limiting and continued metformin use is associated with weight stability.⁴ We have chosen a slow titration up of metformin dosage from 850 mg qd to 850 mg bid to allow for minimization of self-limiting gastrointestinal distress and plan to carefully monitor weight and dietary intake at each study visit. If participants report symptoms of lactic acidosis during screening for adverse events, laboratory confirmation will be sought and study drug cessation if found.

Protection Against Risks of Diagnosis - From labs at Screening and study visits, diabetes may be diagnosed (defined by fasting plasma glucose≥126 mg/dL). Participants will be notified and referred to their primary care physician.

Protection Against Risks of Study Procedures

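### Liver and kidney tests are promised quarterly from age 80, but the visit schedule gives six-monthly kidney tests above 80 and annual liver tests

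*Combined protocol and SAP*

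**What the plan says.** All of the text below is current protocol text.

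- **Protection Against Risks of Metformin Use** commits to "screening liver and kidney function every year in all participants and quarterly in adults aged 80 or greater", and to "stopping metformin in participants who develop evidence of liver/kidney dysfunction for their safety". The two are offered together as protection against lactic acidosis and hepatitis.
- **Half-Yearly Visits**: "Subjects >80 years old will get labs checked for creatinine and eGFR". ALT and AST are not mentioned.
- **Schedule of Study Procedures**, footnote f: every 6 months, "creatinine and eGFR will be obtained for subjects over 80 years old". The ALT and AST rows are marked only at Screening and at Years 1, 2 and 3.
- **Study Procedures, Labs**: blood is collected at Screening, Baseline, half-yearly and annual visits. During follow-up, ALT and AST are listed only among the annual assays. The section has no separate half-yearly rule for older participants.
- **Phone calls between visits**: "At 3 and 9 month time points between annual visits, telephone surveying of medication compliance will be obtained". Adverse events are reviewed on these calls, but no blood is taken.
- **Study Drug**: "A 90-day supply of study drug will be mailed every 3 months to participants".

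**The concern.** The risk section states a safeguard that the operational text cannot supply. No scheduled contact at months 3 or 9 includes a blood draw, so staff who follow the schedule breach the risk section, and staff who try to follow the risk section have no visit at which to do so. The age limit differs as well: 80 or greater in the risk section, over 80 in the visit text and footnote.

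This bears on the participants for whom the extra testing was meant. Entry is open from age 65 with no upper limit, so people of 80 and above can enroll. The protocol's own risk discussion says that metformin accumulation and lactic acidosis become more likely as renal function worsens. Stopping the drug for liver or kidney dysfunction depends on detecting it. Anyone who judges risk from the protection section, including the IRB, is told of closer monitoring of the oldest participants than is planned.

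**Working it through.** The plan gives no total number of tests, so there is no figure to reproduce. The check counts post-baseline tests over the 3-year study for one participant.

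**Stated at age 80 or greater (risk section).** Quarterly means months 3, 6, …, 36: 4 per year × 3 years = 12 kidney and 12 liver checks.

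**Scheduled, over 80 (Half-Yearly Visits, Labs, Schedule and footnote f).**
- Kidney: annual at months 12, 24 and 36 (3), plus half-yearly at months 6, 18 and 30 (3) = 6.
- Liver: annual at months 12, 24 and 36 = 3.

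| | Stated | Scheduled, over 80 | Share | After the fix |
|---|---|---|---|---|
| Kidney checks, 3 years | 12 | 6 | 1/2 | 6 |
| Liver checks, 3 years | 12 | 3 | 1/4 | 6 |
| Longest gap between follow-up kidney tests | 3 months | 6 months | | 6 months |
| Longest gap between follow-up liver tests | 3 months | 12 months | | 6 months |

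The shortfall per person is 12 − 6 = 6 kidney checks and 12 − 3 = 9 liver checks.

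**Early stopping.** Each completed year gives 2 of 4 kidney and 1 of 4 liver checks, so the shares of 1/2 and 1/4 also hold for someone who stops after year 1 (2 of 4, 1 of 4) or year 2 (4 of 8, 2 of 8).

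**Leaving out month 36, when dosing ends.** Stated 12 − 1 = 11; kidney 6 − 1 = 5; liver 3 − 1 = 2.

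**Aged exactly 80.** If over 80 is read strictly, as 81 or more in completed years, the half-yearly kidney test does not apply during that year of age. Kidney checks are then annual: 1 of 4 in that year, not 2 of 4. Half-yearly visits fall 12 months apart, so this normally costs one test, and a three-year total would drop from 6 to 5. If over 80 means past the 80th birthday, nothing changes. The main conflict does not depend on this boundary.

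**Does the general Labs row close the gap?** It is marked at half-yearly visits, but ALT and AST have their own rows with no mark there, and the Labs section assigns them to annual visits.

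**Cost of the fix.** Liver 6 − 3 = 3 added ALT/AST assays per participant aged 80 or more (months 6, 18 and 30). Added visits or needle sticks: 0, because "At each half-yearly visit, all participants will have fasting labwork drawn" and the Labs section already allots 20 mL to each of these visits.

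**The case against.** The case for treating this as minor has weight. Entry criteria already exclude eGFR below 60, raised ALT or AST, heart failure and excess alcohol, which leaves a margin above the eGFR limit of 45 for stopping. Adverse events are reviewed about every three months and "A 24-hour phone number will be provided to participants". Drug is held and renal function rechecked around hospitalization and contrast, reported symptoms of lactic acidosis lead to laboratory confirmation, and a Data Monitoring Committee oversees safety. Several 90-day supplies going out between liver tests is also true of every younger participant under planned annual testing, so it does not measure this inconsistency. All of this stands as mitigation. Most of it is triggered by events or symptoms, however, and it does not replace scheduled tests that the protocol says will be done.

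It can also be said that six-monthly ALT/AST appears nowhere in the plan. That is correct: it is a compromise between two conflicting statements, which is why it needs clinical and IRB confirmation.

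Three stronger readings are tempting but unsupported:

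- *That restart after hospitalization or contrast should be defined by eGFR below 45 alone.* The Labs section relaxes only eGFR, for continuing drug, and keeps every other limit, including creatinine. It does not address restart, and a stricter restart rule is coherent. The choice is clinical.
- *That the list under Criteria for Discontinuation cancels the liver stop because it omits it.* Study Drug and the risk section still require stopping, and the list ends with a general investigator-judgement clause.
- *That the mismatch touches the trial's inference or permits a trial-wide count of missing tests.* No efficacy analysis uses these tests, and the number of participants aged 80 or more is not given.

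**Conclusion.** The inconsistency is real and should be corrected. For a participant over 80 with three years of follow-up, the schedule delivers half of the stated kidney checks (6 of 12) and a quarter of the stated liver checks (3 of 12). While a participant is aged exactly 80, kidney checks also fall to a quarter on a strict reading of the age limit. The annual tests for all participants are scheduled as stated.

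The counts assume that quarterly means every third month from baseline, that all visits are attended, and that the participant is above the age limit throughout; for someone who reaches it during the trial they apply only from then on. They apply in either arm, and 60 of the 120 randomized are assigned to metformin. This is a fault in a safety rule as written. It is not evidence that participants have been harmed.

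**What to change.** Use one rule in Half-Yearly Visits, Labs, the Schedule with its footnote f, and Protection Against Risks of Metformin Use: participants aged 80 or greater have creatinine, eGFR, ALT and AST measured at every half-yearly and annual visit; all others have them at annual visits. Change *quarterly* in the risk section to six-monthly.

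The cost is a protocol amendment, 3 added ALT/AST assays per participant aged 80 or more over three years, and a half-yearly creatinine/eGFR for those aged exactly 80. This assumes that the 20 mL draw leaves enough plasma. The drawback is that the stated frequency falls from 12 to 6 checks per person, so the sponsor's clinicians and the IRB should confirm it. If they want quarterly testing to stand, blood draws must be added at the third and ninth month of each year (12 − 6 = 6 more per person). If they judge six-monthly ALT/AST unnecessary, the minimum is to correct the risk section to the existing schedule.

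One small alignment belongs in the same amendment. The stopping rule under Study Drug points back to the entry exclusions, where the eGFR limit is 60. It should point to the follow-up criteria in the Labs section: eGFR below 45, with the creatinine, liver and B12 limits unchanged. This is a text change only.
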